## 13.4 Reporting of serious adverse events

The criteria that define an AE as serious (that is, an SAE) are defined in [Appendix 1](#). SAE criteria are also listed on the SAE form.

### 13.4.1 Investigator reporting responsibilities

Any SAE must be reported to LEO on the (paper) SAE Form within 24 hours of first knowledge. This report should contain an assessment of available information on seriousness, severity, causal relationship to the IMP (tralokinumab/placebo), IMP (vaccines), IMP device, or trial procedure, the action taken, the outcome to date, and a narrative description of the course of the event.

The completed SAE form must be faxed or scanned and e-mailed to Global Pharmacovigilance at LEO using the e-mail address or fax number below:

#### Global Pharmacovigilance at LEO

E-mail address: [[contact]](mailto:[contact])

[contact]

If relevant, the investigator will enclose other information with the SAE form, such as anonymised reports of diagnostic procedures, hospital records, autopsy reports, etc.

Additionally, Global Pharmacovigilance at LEO may request further information in order to fully assess the SAE. The investigator must forward such information to LEO upon request by fax or e-mail (see contact details above).

The investigator must notify the local IRB(s) of SAEs, as required by current applicable legislation for the concerned country.

SAEs occurring after the completion of the clinical trial (defined as per Section [7.3](#)) should not be routinely sought or collected. However, such events should be reported to Global

Pharmacovigilance at LEO (see contact details above) if the investigator becomes aware of them.

### 13.4.2 LEO reporting responsibilities

Global Pharmacovigilance at LEO is responsible for assessing whether or not an SAE is expected. The relevant reference safety information documents for this clinical trial are:

- For the IMP (tralokinumab/placebo), the Investigator's Brochure, edition 17 and subsequent updates must be used.
- For the IMP (Tdap and meningococcal vaccines), the latest version of the approved labelling in the US must be used.

Global Pharmacovigilance at LEO will notify the regulatory authorities and concerned investigators of SAEs according to the current applicable legislation for the concerned countries.

The IRB(s) will be notified of SAEs according to the current applicable legislation for the concerned countries.

For all countries except the US, the following reporting requirements apply: all SAEs which are assessed as causally related to the IMP(s) **by either the investigator or LEO** (ICH E2A Guideline), and which are unexpected (Suspected, Unexpected Serious Adverse Reactions [SUSARs]), are subject to expedited reporting to regulatory authorities and IRB(s) according to the current applicable legislation in the concerned countries. Investigators will be notified of the evolving safety profile of the IMP on an ongoing basis.

For the US, the following reporting requirements apply: all SAEs which are assessed as causally related to the IMPs **by LEO** (Guidance for Industry and Investigators - Safety Reporting Requirements for INDs and BA/BE Studies; Guidance for Clinical Investigators, Sponsors, and IRBs: Adverse Event Reporting to IRBs – Improving Human Subject Protection) and which are unexpected (Serious and Unexpected Suspected Adverse Reactions [IND safety report]) are subject to expedited reporting to regulatory authorities and IRB(s). Investigators will be notified of the evolving safety profile of the IMP on an ongoing basis.

## **13.5 Other events that require expedited reporting**

### **13.5.1 Pregnancy**

Any pregnancy occurring during the clinical trial must be reported to LEO within 24 hours of first knowledge using the (paper) Pregnancy Form (Part I). All pregnancies must be followed up until delivery or termination and final outcome must be reported on the (paper) Pregnancy Form (Part II) within 24 hours of first knowledge.

The completed Pregnancy Forms must be faxed or scanned and e-mailed to Global Pharmacovigilance at LEO. Contact details are given in Section [13.4.1](#).

Pregnant subjects must immediately discontinue IMP permanently (Sections [10.2.1](#) and [10.3](#)).

## **13.6 Reporting of other events**

### **13.6.1 Adverse events of special interest**

The events listed in [Panel 12](#) are considered AESIs in this trial and will require additional details to be recorded in the eCRF. LEO may also request that the investigator forward test results, if applicable. An AESI may be serious (requiring expedited reporting, Section [13.4](#)) or non-serious.

**Panel 12: Adverse events of special interest**

Adverse event of special interest	Additional information to be provided
Eczema herpeticum	Skin findings: 
 
• Lesion type (papules, vesicles, crusts, eroded pits, other).
 
• Disseminated / localised.
 
• Location (face, scalp, back, chest, upper limb, lower limb, genitals).
 
• Present in an area with visible eczema / no visible eczema / present in areas with and without eczema.
 
• Monomorphic / polymorphic.
 
 Confirmation of herpes simplex virus (not confirmed, PCR, viral culture, Tzanck, other)
Malignancies diagnosed after randomisation, excluding basal cell carcinoma, localised squamous cell carcinoma of the skin, and carcinoma in situ of the cervix	
 
• Histology report available
 
• Oncology assessment available
 
• Treatments (surgery, radiation, chemotherapy, other)
 

Skin infections requiring systemic treatment	
 
• Location (face, scalp, back, chest, upper limb, lower limb, genitals)
 
• Outcome of pathogenic skin swab (positive, negative, not performed)
 

Conjunctivitis	
 
• Aetiology (viral, bacterial, allergic, unknown)
 
• Bacterial culture outcome (for events with bacterial aetiology)
 
• Diagnosis confirmed by ophthalmologist
 

Keratoconjunctivitis	
 
• Aetiology (infectious, non-infectious, other, unknown)
 
• Bacterial culture outcome (for events with bacterial aetiology)
 
• Diagnosis confirmed by ophthalmologist
 

Keratitis	
 
• Aetiology (infectious, non-infectious, other, unknown)
 
• Bacterial culture outcome (for events with bacterial aetiology)
 
• Diagnosis of herpes simplex keratitis (for events with viral aetiology)
 
• Diagnosis confirmed by ophthalmologist
 

### 13.6.2 Overdose

An overdose is defined as a subject receiving a dose of IMP in excess of that specified in this protocol.

The term ‘overdose’ must be recorded on the AE form of the eCRF. In addition, AEs originating from overdose must be recorded as separate events. If an AE originating from an overdose qualifies as an SAE, expedited reporting is required (Section 13.4).

LEO does not recommend specific treatment for an overdose. The investigator will use clinical judgment to treat any overdose if necessary.

### 13.6.3 Medication error

Medication error refers to any unintentional error in the dispensing or administration of an IMP while in the control of the investigator or subject. Broadly, medication errors fall into 4 categories: wrong medication, wrong dose (including strength, form, concentration, amount), wrong route of administration, or wrong subject.

The medication error category must be recorded on the AE form in the eCRF. In addition, AEs originating from a medication error must be recorded as separate events. If an AE originating from the medication error qualifies as an SAE, expedited reporting is required (Section 13.4).

If the medication error is due to a device deficiency, the device deficiency must be reported as a product complaint as described in Section 9.10.

### 13.6.4 Misuse

Misuse refers to situations where the IMP is intentionally and inappropriately used not in accordance with the protocol.

The term ‘misuse’ must be recorded on the AE form in the eCRF. In addition AEs originating from misuse must be recorded as separate events. If an AE originating from misuse qualifies as an SAE, expedited reporting is required (Section 13.4).

### 13.6.5 Abuse

Abuse relates to the sporadic or persistent, intentional excessive use of an IMP which is accompanied by harmful physical or psychological effects.

The term ‘abuse’ must be recorded on the AE form in the eCRF. In addition, AEs originating from abuse must be recorded as separate events. If the AE originating from abuse qualifies as an SAE, expedited reporting is required (Section 13.4).

### 13.6.6 Aggravation of condition

Any clinically significant aggravation/exacerbation/worsening of any medical condition(s), compared to screening, must be reported as an AE in accordance with Section 13.3. If the AE originating from aggravation of condition qualifies as an SAE, expedited reporting is required (Section 13.4).

### 13.7 Follow-up for final outcome of adverse events

During the trial, the investigator should follow up for final outcome on all AEs (including SAEs). Once a subject leaves the clinical trial, the investigator should follow up on the outcome of all non-serious AEs classified as of possible/probable relationship to the IMP for 2 weeks or until the final outcome is determined, whichever comes first. SAEs must be followed up until a final outcome has been established, that is, the follow-up may continue beyond the end of the clinical trial. For SAEs which have stabilised and cannot be expected to recover during study or safety follow-up periods, for example chronic illnesses, the final outcome should be reported as ‘not recovered’. In addition, a statement that the SAE has stabilised or is chronic should be added to the narrative description of the SAE on the SAE form.

### 13.8 Handling of an urgent safety measure

An urgent safety measure is a measure taken to implement an action/protocol deviation under an emergency. This is defined as “...*the occurrence of any new event relating to the conduct of the trial or the development of the investigational medicinal product where that new event is likely to affect the safety of the subjects, the sponsor and the investigator shall take appropriate urgent safety measures to protect the subjects against any immediate hazard.*” (35).

If the investigator becomes aware of information that necessitates an immediate change in the clinical trial procedure or a temporary halt to the clinical trial in order to protect clinical trial subjects from any immediate hazard to their health and safety, the investigator can do so without prior approval from LEO, regulatory authorities, or IRBs.

The investigator must immediately inform LEO – by contacting the clinical project manager or medical expert – of this change in the clinical trial procedure or of the temporary halt

providing full details of the information and the decision making process leading to the implementation of the urgent safety measure.

LEO must act immediately upon receipt of the urgent safety measure notification in accordance with internal procedures and local legislation.

## 14 Statistical methods

### 14.1 Sample size

A total of 200 subjects will be randomised 1:1 to tralokinumab or placebo to ensure that a sufficient number of subjects complete the trial and fulfil the definition of the per protocol set which is considered the primary analysis set for establishing non-inferiority between tralokinumab and placebo with regard to immune responses to vaccines.

With 200 subjects in the FAS and 160 subjects anticipated in the per protocol set, the trial will provide 98% power to establish non-inferiority with regard to positive anti-tetanus response based on a one-sided significance level of 2.5%, assuming a response rate of 80% in both arms and a non-inferiority margin of -25%. Assuming a positive anti-meningococcal response rate of 80% in both arms, an IGA 0/1 response rate of 30% (tralokinumab) versus 10% (placebo), and an EASI75 response rate of 40% (tralokinumab) versus 15% (placebo), the trial will provide approximately 89% power for rejecting all 4 hypotheses related to the primary and secondary endpoints with each hypothesis tested at a one-sided 2.5% significance level. This evaluation is assuming no correlation between the primary and secondary endpoints.

To our knowledge there is no established margin in the literature for showing non-inferiority with regard to immune responses to vaccines and the sample size of previously conducted trials with similar objective varies. In a similar type of trial with dupilumab versus placebo in adults with moderate-to-severe atopic dermatitis (36), a total of 194 subjects was randomised (1:1) to assess vaccine response but no non-inferiority margin was pre-specified. By contrast, in a trial with ixekizumab versus placebo in healthy subjects, a total of 84 subjects were randomised (1:1) and a non-inferiority margin of -40% was pre-specified (ClinicalTrials.gov NCT02543918). Similarly, a non-inferiority margin of -40% was pre-specified in a trial with secukinumab versus placebo in healthy subjects (37).

On the basis of knowledge from previous trials, the proposed sample size and non-inferiority margin of -25% is considered appropriate to assess the primary objective of the trial.

### 14.2 Trial analysis sets

All screened subjects will be accounted for in the CTR.

All subjects randomised to treatment are included in the FAS and will be analysed for efficacy up to Week 16. Exclusions from the FAS can be considered in special cases as described in

ICH E9, Section 5.2.1, Full Analysis Set. If it is decided to exclude a randomised subject from the FAS, a justification addressing ICH E9 will be given.

A per protocol analysis set will be defined by excluding subjects from the FAS for whom any of the following conditions apply:

- Receive no treatment with the IMP (vaccines).
- Provide no vaccine data at Week 16.
- Are known to have taken the wrong IMP throughout the treatment period.
- Do not fulfil the inclusion criteria no. 3, 6, 7, 8.
- Meet exclusion criterion related to receipt of other vaccines (that is, exclusion criterion no. 10).
- Initiate systemic rescue treatment prior to Week 10 and who are still treated with or exposed to systemic rescue treatment at Week 10 (that is, Week 10 [visit 8] occurs within 5 half-lives after the last dose of systemic rescue medication).
- Initiate systemic rescue treatment at Week 10 or later.
- Have missed more than 2 doses of tralokinumab/placebo before vaccine administration.
- Have missed any of the last 2 doses of tralokinumab/placebo before vaccine administration (that is, Weeks 8 and 10).

The per protocol analysis set will be used as primary analysis set for the vaccine antibody responses at Week 16 (primary endpoints; Panel 13). For the secondary endpoints (IGA 0/1 and EASI75 at Week 16), the FAS analysis will be considered primary.

A safety analysis set will be defined by excluding subjects from the FAS who received no treatment with IMP.

Based on the above-mentioned rules, the inclusion/exclusion of subjects or subject data from the trial analysis sets will be documented in the statistical analysis plan update before breaking the randomisation code.

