#### **9.8.4 Treatment compliance**

All IMP injections (tralokinumab/placebo and vaccines) will be performed by site staff who will also keep the accountability records up to date. Any non-compliance (subject received partial dose; subject received no dose) and the reason for the non-compliance will be recorded in the eCRF.

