The safety analysis set comprises all subjects randomised to treatment who were exposed to IMP. The protocol further specifies to exclude subjects from the safety analysis set for whom no post-baseline safety data are available. However, since all subjects receive the first dose of IMP in connection with the Week 0 visit and are subsequently monitored for immediate drug reactions, all exposed subjects are considered to have post-baseline safety data available and no such further exclusions will be made.

In addition to the analysis sets defined in the protocol, a safety follow-up analysis set will be used as the basis for evaluation of adverse events during the safety follow-up period. It comprises all subjects for whom date of last contact is after the date of exposure end, where exposure end is defined as the Week 16 visit for subjects completing the treatment period, and otherwise the date of permanent discontinuation of IMP (tralokinumab/placebo) for subjects not completing the treatment period. See also Section 6.9.2 for further details.

For analysis of efficacy, subjects will be included 'as randomised'.

For analysis of safety, if a subject is mistakenly given an IMP other than that to which they were randomised, they will be analysed 'as treated', thus included in the group according to the therapy actually received by the subject. The below rules will be applied.

Subjects who received at least one dose of tralokinumab will be analysed in the tralokinumab treatment group. Although this may dilute the AE rate in the tralokinumab treatment group slightly by including in the denominator subjects who only received one dose of active treatment, it will ensure that no significant drug reactions to tralokinumab will erroneously be assigned to placebo.

The definition of the per protocol analysis set as described in the protocol has been updated to accept negligible deviations in baseline disease severity related to the EASI status. Thus, the criteria from inclusion criterion 7 have been modified to require an EASI score of ≥ 12 at screening OR ≥ 16 at baseline instead of requiring both criteria to be met. The rationale for this change is that marginal deviations in baseline disease severity is not considered to affect the vaccine response.

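### The per-protocol set removes subjects for missed doses before vaccination but, read literally, keeps subjects given the other arm's product at those same visits

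*Protocol*

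**What the plan says.** Protocol 14.2 (Trial analysis sets) makes the per-protocol set primary for the vaccine endpoints: "The per protocol analysis set will be used as primary analysis set for the vaccine antibody responses at Week 16". Three of its exclusions concern the tralokinumab/placebo injections:

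- Wrong product: subjects who "Are known to have taken the wrong IMP throughout the treatment period".
- Cumulative missed doses: subjects who "Have missed more than 2 doses of tralokinumab/placebo before vaccine administration".
- Last doses before vaccination: subjects who "Have missed any of the last 2 doses of tralokinumab/placebo before vaccine administration", which the protocol identifies as Weeks 8 and 10.

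Protocol 9.8.4 describes what is recorded as non-compliance in terms of a partial dose or no dose. A full dose of the wrong product is not listed there. Protocol 13.6.3 does recognise it, as a medication-error category recorded on the AE form: "Broadly, medication errors fall into 4 categories: wrong medication, wrong dose".

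SAP section 5 changes the per-protocol set in three respects: the EASI entry criterion, systemic immunosuppressants for any indication, and a Week 12 to Week 16 interval of 56 days or more. It does not change the wrong-product rule. The same section provides for dosing errors in the safety analysis, "if a subject is mistakenly given an IMP other than that to which they were randomised", where subjects are grouped by the product received. Efficacy is analysed by randomised arm. Neither document states an arm-assignment rule specifically for the vaccine endpoints, which have their own section (SAP 6.6), separate from efficacy (SAP 6.7).

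**The concern.** The missed-dose rules tie membership of the set to exposure in the weeks before vaccination. A dose of the other arm's product also departs from the assigned exposure, but it triggers an exclusion only if it happened throughout treatment. An error confined to a few visits therefore falls outside all three rules when they are read literally.

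The clearest case is a placebo subject given tralokinumab, who is exposed to the drug under test while being counted as a control. A tralokinumab subject given placebo is pharmacologically close to one who missed the dose, and a reader could treat the dose as missed.

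If tralokinumab lowers vaccine response, mixing the arms pulls the observed difference towards zero, and in a non-inferiority test that favours the claim. The full-analysis-set analysis in Protocol 14.3.5 would keep the same subjects, so neither planned analysis of the primary endpoints removes the mixing.

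**Working it through.** **Inputs from the documents.** Protocol 14.1: 160 subjects anticipated in the per-protocol set, taken as 80 per arm under 1:1 allocation; 80% response in both arms; margin -25 points; one-sided 2.5%. Protocol 8.2: 16 weeks equals 5 half-lives, so one half-life is 16/5 = 3.2 weeks.

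**Assumption.** The documents give no number of subjects with partial wrong product. I use 0 to 8 per arm.

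**Step 1: reproduce the stated power.** SE = sqrt(2 × 0.8 × 0.2 / 80) = 0.0632. Power = Φ(0.25/0.0632 − 1.96) = 97.7%. Exact binomial enumeration with a Wald 95% interval gives 97.6%. The protocol's 98% reproduces.

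**Step 2: shift in the expected difference.** Put the truth at the margin: placebo 80%, tralokinumab 55%. One full switch moves the expected difference by 0.25/80 = 0.31 points towards zero. With k full switches in each arm it is −25 + 2k × 0.3125 points.

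**Step 3: false non-inferiority rate.** Exact binomial enumeration, 80 per arm, unstratified Wald 95% interval, switched subjects counted in their randomised arm. In the half-effect column a switched subject moves only half-way to the other arm's response rate.

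| Switched subjects | Expected difference, full effect | Rate, full effect | Rate, half effect |
|---|---|---|---|
| None | −25.0 | 2.4% | 2.4% |
| 1 in one arm | −24.7 | 2.7% | 2.5% |
| 1 per arm | −24.4 | 2.9% | 2.7% |
| 2 per arm | −23.8 | 3.5% | 2.9% |
| 4 per arm | −22.5 | 5.1% | 3.6% |
| 8 per arm | −20.0 | 9.8% | 5.1% |

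Two full switches in the same arm give 2.9%, as does one per arm.

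**Step 4: is a Week 8 and 10 swap a full switch?** Take a simple one-compartment sum with a 3.2-week half-life and 300 mg as one unit. Each dose contributes dose × 0.5^((12 − week)/3.2) at Week 12, before that visit's injection.

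- Day 0 (two units) 0.149; Week 2 0.115; Week 4 0.177; Week 6 0.273; Week 8 0.420; Week 10 0.648. Total 1.78.
- Placebo subject given tralokinumab at Weeks 8 and 10: (0.420 + 0.648)/1.78 = about 60% of full exposure.
- Tralokinumab subject given placebo at those visits: about 40% remains.
- A swap at Week 10 only: 0.648/1.78 = about 36% of full exposure.

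Such a swap is therefore a partial switch. If response moved in proportion to exposure, which is an assumption, its effect would be nearer the half-effect column than the full one.

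**Step 5: cost of excluding.** By the formula in Step 1, power is 97.4% with 2 subjects removed per arm (78 left), 97.1% with 4 (76 left) and 96.3% with 8 (72 left).

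**The case against.** The strongest reply is that the event is hypothetical and controlled. The IRT assigns individually numbered kits at each visit, the products look different and are given by an unblinded professional, and accountability is checked by the monitor (Protocol 9.2.1, 9.3.1, 9.8.3). Wrong product at both Week 8 and Week 10 would need two separate errors. This stands, and it is why the point is minor.

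A second reply is that a missed dose can be read as failure to receive the assigned dose, which would cover a tralokinumab subject given placebo. Protocol 9.8.4 describes eCRF recording; it does not define the term for the analysis set. The reading is fair for that direction of error. It fits poorly for a placebo subject given tralokinumab, and neither document adopts it.

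A third is that Protocol 14.3.10 provides for review of the analyses against blinded data, with changes through the SAP update, and the SAP used that route for three other per-protocol rules. A reader might infer that blinded review could not touch such a subject, since Protocol 14.2 ties set decisions to its listed rules. That goes too far: the route existed, but it was not used for this rule.

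A reader might also infer that these subjects will certainly be analysed in their randomised arm. The SAP says so for efficacy only. Applying it to the vaccine endpoints is an inference, though no other rule is offered. Nor do the documents say that the per-protocol set was made primary in order to prevent dilution of this kind.

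**Conclusion.** The gap in the wording is real, the SAP does not close it, and it works in the direction that favours non-inferiority. It is a minor point. With one or two affected subjects, the false non-inferiority rate is about 2.5% to 2.9%, against 2.4% with none.

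A reader might conclude that the error rate doubles. That needs four full switches in each arm, eight subjects in all. Nothing in the documents suggests that number, and a Week 8 and 10 swap is only a partial switch.

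The figures rest on four assumptions: true rates of 80% and 55%, 80 subjects per arm, an unstratified Wald interval in place of the planned stratified Mantel-Haenszel one, and analysis by randomised arm. If tralokinumab has no effect on vaccine response, the swap causes no bias. The protocol's sample size and stated power are not affected.

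**What to change.** In the SAP's per-protocol definition, count a known wrong-product dose of tralokinumab/placebo before vaccination as a missed dose. A subject is then excluded if more than two pre-vaccination doses, or the Week 8 or Week 10 dose, were missed or were the wrong product. Report the number affected by arm.

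This matches the scope of the existing missed-dose rules, which stop at vaccination. It leaves wrong product at Weeks 12 and 14 where those rules leave missed doses.

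The cost is possibly one or two subjects; even two per arm lowers power only from 97.7% to 97.4%. It also needs a reconciliation step. Kit numbers are in the eCRF (Protocol 9.8.3) and wrong-medication errors are on the AE form (Protocol 13.6.3), but a kit mismatch does not tell blinded staff which product the kit held. Staff who are already unblinded would have to check this and pass on only the exclusion decision, so that set membership is fixed before the randomisation code is broken, as Protocol 14.2 requires.
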